12.4. Procedures for Reporting Serious Adverse Events

It is the responsibility of the local investigator to ensure that all adverse events which fall in to the category of Serious Adverse Events (SAEs) are reported to NHSBT Clinical Trials Unit, Chief Investigator, central investigators and, if required, to their local R&D department as soon as possible after becoming aware of the event but no later than 24 hours. AE not meeting the definition for serious will not be collected.

Data will include but not be limited to:

- A description of the event
- The dates of the onset and resolution
- Action taken
- Outcome
- Assessment of relatedness to the trial procedures, conduct or intervention
- How the event qualifies as serious
- Expectedness

The severity of events will be assessed on the following scale: 1 = mild, 2 = moderate, 3 = severe.

Adverse events that occur during the course of the study should be treated by established standards of care that will protect the life and health of the study subjects.

Serious adverse events will be collected from transplant until 12 months following the transplant, via a purposely designed MACRO database (access via www.ctu.nhsbt.nhs.uk/macro). SAEs will be automatically notified to NHSBT CTU. If the eCRF is unavailable for any reason, a paper version of the form should be completed, scanned and emailed to serious adverse [contact]. Within the following 5 working days, the local investigator may be required to provide additional information on the SAE in the form of a written narrative. This should include a copy of the completed SAE form, and any other diagnostic or relevant information that will assist the understanding of the event.

Additional and further requested information (follow-up or corrections to the original case) should also be added to eCRF using a new SAE Report Form. NHSBT CTU will ensure that all SAEs are reported to the Sponsor .

The clinical reviewers will review the SAEs and, if they feel they pose an immediate risk to patient health or safety, then they will report them to the DMC immediately, and the REC within 15 calendar days of the Chief Investigator becoming aware of the event. This includes any SAEs that the local investigator assesses to be unexpected and related to the study procedure.

Clinical Trial Protocol Template version 14.0

CONFIDENTIAL

© Copyright: The University of Oxford and Oxford University Hospitals NHS Foundation Trust 2018

All SAEs will be followed up to resolution. The DMC will review the accumulating data at regular intervals.

.

12.5. Study Suspension or Early Termination

The DMC or sponsor may recommend suspension or termination of the study either at an individual investigation site or the entire study for significant and documented reasons. An investigator, ethics committee or regulatory authority may suspend or prematurely terminate participation in the study at the investigation sites for which they are responsible. If suspicion of an unacceptable risk to subjects arises during the study, or when so instructed by the ethics committee or regulatory authorities, the sponsor shall suspend the study while the risk is assessed. The sponsor shall terminate the study if an unacceptable risk is confirmed.

The sponsor shall consider terminating or suspending the participation of a particular study site or investigator in the study if monitoring or auditing identifies serious or repeated deviations on the part of an investigator.

If suspension or premature termination occurs, the terminating party shall justify its decision in writing and promptly inform the other parties with whom they are in direct communication. The chief investigator and sponsor shall keep each other informed of any communication received from either the ethics committee or the regulatory authority.

If, for any reason, the sponsor suspends or prematurely terminates the study at an individual investigation site, the sponsor shall inform the responsible regulatory authority as appropriate and ensure that the Ethics Committee is notified, either by the chief investigator or by the sponsor. If the suspension or premature termination was in the interest of safety, the sponsor shall inform all other investigators.

If suspension or premature termination occurs,

- a) the research team remain responsible for providing resources to fulfil the obligations from the study protocol and existing agreements for following up the subjects enrolled in the study, and
- b) the chief investigator or authorized designee shall promptly inform the enrolled subjects at their study site, if appropriate.

Device deficiencies and use errors should be reported directly to Organox for investigation by the manufacturer.

SAE reporting will continue until the last patient recruited has completed 12 months of follow-up. Patients transferred back for on-going care to referring centres will have their data including AEs related to the outcome measures collected by data collection forms sent to the patient's specialist. Patient cards will be provided to all participants of the study, with a contact telephone number (research nurse / researcher) to inform regarding the occurrence of SAEs.

13. STATISTICS

13.1. Statistical Analysis Plan (SAP)

The statistical aspects of the study are summarised here with details fully described in a separate statistical analysis plan. The SAP will be finalised before any analysis takes place.

13.2. Description of Statistical Methods

Primary outcome reporting will occur after collection and analysis of data at 12 months following the enrolment of the last patient to the trial. The outcome measures are described in detail in section 6.

The study arm (NMP) will be compared against RWC cohort (SCS) defined in Section 8.1 at this point for all primary and secondary outcomes, except 5 year outcomes. 95% confidence intervals will be provided for all assessments of treatment effect. Baseline characteristics of the donors enrolled and transplanted will be presented separately, together with characteristics of the liver transplant recipients. A CONSORT diagram will show the flow of donor livers and recipients through the study, in particular the reasons for any post-enrolment exclusions which are necessary because study entry occurs before some exclusion criteria can be assessed.

The primary outcome is a binary outcome of functional utilisation at 12 months. As the 12-month visit may occur at a routine hospital appointment prior to 12 months, livers will be assumed to be functioning at 12 months if documented as functioning >10 months post-transplant. The primary outcome will be analysed using a logistic regression model to assess the effect of treatment on outcome, after adjustment for the important prognostic factors of donor type and use of normothermic regional perfusion (NRP). The odds ratio, 95% confidence interval and p-value for the treatment term in this logistic regression model will be the primary analysis for the trial. NMP will be concluded superior if the lower bound of the confidence interval exceeds the efficacy threshold which has been pre-specified at 40 extra livers transplanted with one-year function per year (an OR of 1.20).

Secondary outcomes will be presented using descriptive statistics and analysed using a similar approach, with adjustment for donor type and use of NRP. However, when performing analyses on the subset of transplanted livers, adjustment will also be made for the transplanting centre where numbers allow. General Linear and Generalised Linear Models or non-parametric methods will be used as appropriate for the different outcomes. Length of HDU/ITU and hospital stay post-transplant will be analysed using a competing risks approach where death is the competing risk. Measures of biochemical liver function at 12 months will be compared between the two treatment arms using linear regression, with appropriate transformation if required. Patient and graft survival (censored and non-censored) will be estimated using the Kaplan-Meier method and analysed using Cox Proportional Hazards regression. Safety outcomes will be summarised for each arm according to classification and severity. Some outcomes are only measured in the study arm and these will be presented using descriptive statistics. Measures of biochemical liver function over the first seven days will be presented graphically and area under the curve summarised for the study arm, along with a summary of the MEAF score.

During the trial, data will be collected regarding perfusion parameters (including machine logs and perfusate characteristics). These data will be analysed separately to the main clinical trial outcomes to explore relationships between perfusion parameters, utilisation and transplant outcomes.

Clinical Trial Protocol Template version 14.0

CONFIDENTIAL

© Copyright: The University of Oxford and Oxford University Hospitals NHS Foundation Trust 2018

After the final patient has reached five years post-transplant, patient and graft survival will be obtained from the transplant registry. The unadjusted survival rates at five years will be estimated using the Kaplan-Meier method. A Cox proportional hazards model will also be used to assess the treatment effect after risk-adjustment for any imbalance in baseline characteristics that is known to affect recipient outcome.

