8.3. Inclusion Criteria

Liver offers:

- Deceased organ donors aged 16 years or over
- Offered through the national offering scheme
- Donor Utilisation Index (DUI) greater than 0.27

Liver transplant recipients:

- Recipients 18 years of age or above
- Elective and super-urgent
- Participant is willing and able to give informed consent for participation in the study

Livers undergoing normothermic regional perfusion (NRP) will be included in the study and use of NRP corrected for in analysis.

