13.3. Sample Size Determination

There are 2465 livers in the retrospective control cohort. One-year functional utilisation in this group was calculated using complete organ utilisation data and a Kaplan-Meier estimate of transplant survival at one year, due to a small proportion of censored data prior to that point. One year functional utilisation in the control cohort was 21.8%. A 50% improvement in functional utilisation (to 32.7%) would represent an increase of around 135 extra transplants functioning at 1 year each year in the UK. This would transform waiting list mortality (50 patients in 2019-20) and average waiting times.

There will be some circumstances where, typically due to logistics (e.g. temporary NMP unavailability), centres will preserve a liver in the NMP study cohort using SCS. In the European Phase-3 trial, only one liver randomised to NMP crossed-over to the SCS arm (14). This figure is likely to be higher in the current study due to earlier study entry and logistical constraints, so we have allowed for a 15% crossover rate (25% due to logistical reasons, 5% eligibility message not relayed and 5% general cross-over). We will analyse the data on a modified ITT basis, whereby livers unable to be perfused for logistic reasons are excluded, along with those who were found to be ineligible after study entry.

Allowing for these exclusions and cross-over rate, the sample size was calculated based on an anticipated increase in the primary endpoint from 21.8% in the RWC cohort to 31.4% in the NMP mITT analysis. A 'superiority by a margin' design was used, such that with a 2.5% one-sided significance level the sample size will have 90% power to detect whether NMP is superior to SCS by the prespecified threshold (margin) of 40 extra livers transplanted with one year function per year. As there are 2465 livers in the control cohort, an allocation ratio of 3.5:1 was used to achieve the necessary power and this requires a sample size of 700 liver offers in the NMP study arm. As the primary endpoint uses mandatory data collected by NHSBT, loss to follow-up should be low. Allowing a 25% loss due to exclusions due to being unable to use NMP for logistical reasons and another 10% loss (due to withdrawal of consent, loss to follow-up and those meeting exclusion criteria after study entry), the number required increases to 1035 offers.

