25. APPENDIX 3: DONOR UTILISATION INDEX (DUI)

The Donor Utilisation Index (DUI) is a clinical risk score that estimates the risk of non-utilisation of an offered liver. It was derived from analysis of a cohort UK liver offers between 1 February 2016 and 31 January 2020. The overall sample was randomly split into model development and validation cohorts, and separate models were derived for DBD (development n=2,590, validation n=1,067) and DCD (development n=1,746, validation n=758) donors. 26 candidate variables were considered, and those statistically significant at the 10% level were included in the final model.

Both models showed good performance, with a C-statistic of 0.78 for the DBD model, and 0.796 for the DCD model.

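### The primary model leaves out DUI, so a change in donor risk above the 0.27 cut-off between the two eras goes uncorrected in the decision against OR 1.20

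*Protocol*

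**What the plan says.** Section 13.2 names the covariates of the model whose treatment term is the primary analysis: "after adjustment for the important prognostic factors of donor type and use of normothermic regional perfusion (NRP"). The decision threshold in the same section is "pre-specified at 40 extra livers transplanted with one-year function per year (an OR of 1.20"). Section 8.3 also commits to having "use of NRP corrected for in analysis", and section 13.2 carries the same covariates to the secondary outcomes, which are "analysed using a similar approach, with adjustment for donor type and use of NRP".

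Of DUI, Appendix 3 says: "The Donor Utilisation Index (DUI) is a clinical risk score that estimates the risk of non-utilisation of an offered liver". Its C-statistics there are 0.78 (DBD) and 0.796 (DCD). Section 9.2 has it calculated automatically at the matching run, before any centre receives the offer, and section 8.1 used the same formulae to select the controls.

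In the analysis, DUI appears by name only as a quartile subgroup (section 13.4). Adjustment for baseline differences is assigned to a propensity-matched analysis, which sections 7 and 13.4 call secondary.

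**The concern.** The controls were offered between January 2018 and December 2019, and study recruitment was planned for April 2022 to October 2023. Nothing but the entry criteria makes the cohorts alike. A common lower limit on DUI says nothing about how risk is distributed above that limit, so the two cohorts may differ in mean DUI, and the difference passes into the treatment odds ratio.

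The protocol accepts that DUI mix matters. Section 8.1 keeps 118 machine-perfused controls because they had lower DUI and dropping them would have biased the cohort. Yet the decision-bearing model has no term for DUI. A matched analysis may reveal a discrepancy but cannot correct the primary decision.

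NRP raises a second question. The outcome is counted over all offers, including those declined. Section 9.3 places retrieval after acceptance. If NRP is done at retrieval, a liver declined by every centre beforehand is recorded as having had no NRP, and the covariate partly marks acceptance, a step that section 7 includes in the impact of NMP being assessed.

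**Working it through.** **1. The plan's own figures.** Section 13.3 plans for an increase "from 21.8% in the RWC cohort to 31.4% in the NMP mITT analysis", and "with a 2.5% one-sided significance level the sample size will have 90% power"; "an allocation ratio of 3.5:1 was used to achieve the necessary power and this requires a sample size of 700 liver offers".

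- Margin: 2465 controls over two years is 1232.5 a year; 40/1232.5 = 3.25 percentage points. Threshold rate: 21.8% + 3.25% = 25.05%.
- As an odds ratio: (0.2505/0.7495)/(0.218/0.782) = 1.20, as stated.
- n = (1.960 + 1.282)² × [0.314×0.686 + 0.218×0.782/3.5]/(0.096 − 0.03245)² = about 687, within 2% of 700.

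The sample size reproduces and is not in dispute. Note that 1.20 is a marginal odds ratio, derived from two overall rates.

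**2. Effect of a DUI shift with no NMP effect.** Assumed, because the protocol gives none of it: within DUI above 0.27, x = −(logit-DUI minus its control mean) is normal with SD 0.8 to 1.3, and P(functional utilisation) = expit(a + x), slope 1. The constant a is set so that the control mean is 21.8%. In the study cohort the mean of x is raised by d, so DUI is lower. Donor type and NRP are ignored. Extra livers = (rate − 0.218) × 1232.5.

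| SD | d | Study rate | OR | Extra livers a year |
|---|---|---|---|---|
| 0.8 | 0.1 | 23.4% | 1.09 | 19 |
| 0.8 | 0.2 | 25.0% | 1.20 | 40 |
| 1.3 | 0.1 | 23.2% | 1.08 | 17 |
| 1.3 | 0.2 | 24.6% | 1.17 | 35 |

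If instead the true effect sits exactly at the threshold (nominal error 2.5%) and the log-odds slope is 0.4 to 1.0 per SD of DUI, a study-cohort DUI 0.1 SD lower gives a 5.7% to 13.4% chance of declaring superiority. At 0.2 SD lower it is 11.8% to 41.2%. A shift to higher DUI works the other way.

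**3. What adding DUI does to the margin.** The odds ratio is non-collapsible. The change from 21.8% to 25.05% corresponds to this DUI-conditional OR:

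- about 1.20 at slope 0.4 per SD;
- 1.22 at logit-DUI SD 0.8 (slope 1);
- 1.26 at SD 1.3 (slope 1).

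Testing a DUI-adjusted OR against an unchanged 1.20 would raise the one-sided error at the threshold from 2.5% to about 3.7% (SD 0.8) or 6.2% (SD 1.3), even with perfectly balanced cohorts.

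**4. The NRP term.** Assumed: 22% of DCD offers accepted; 62% of those functioning at 12 months; NRP only in accepted DCD livers, in 10% of them in controls and 30% in the study; no effect of NRP or NMP. Among DCD offers without NRP, the success rates are:

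- control: 0.22×0.9×0.62/(1 − 0.22×0.1) = 12.6%;
- study: 0.22×0.7×0.62/(1 − 0.22×0.3) = 10.2%.

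That is an OR of 0.79 in this stratum, against 1.00 among NRP livers and among DBD offers. The fitted treatment OR is 1.00 without the NRP term and 0.93 (50% DCD) to 0.90 (70% DCD) with it. NRP itself acquires a spurious OR of about 12.

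A variant without donor type (35% accepted, NRP share rising from 5% to 20% or 30%) gives 0.87 or 0.79. With a true NMP effect and equal NRP shares of 8% or 20%, the distortion is small: 1.64 becomes 1.62, or 1.65 becomes 1.60.

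**The case against.** Case-mix is not ignored. Both cohorts are consecutive offers under the same rule, donor type is a valid pre-offer covariate already in the model, a propensity-matched analysis is pre-specified, and DUI and DLI subgroups are planned. This stands, but none of it enters the comparison with 1.20.

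The magnitudes are hypothetical. No spread, slope or drift of DUI is given, and the C-statistics describe utilisation over the whole DUI range, not 12-month functional utilisation above 0.27. That also stands: the figures show sensitivity, not an estimated bias. A reader might infer that the primary OR favours NMP. The documents do not support a direction. Section 5.1 describes offered donors as becoming more marginal, and if that continued, leaving out DUI would hide benefit.

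On NRP, a reader might infer that the adjustment is simply wrong and should be dropped. The protocol does not state when NRP takes place; the order is inferred from section 9.3. Section 9.7.2 provides for declines after retrieval, so NRP use does not imply transplantation. The distortion shown runs against NMP and depends on assumed NRP shares. There is also a reason for the term: if NRP improves outcome and its use rose, omitting it would credit that gain to NMP.

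A reader might also extend the point to the recipient outcomes. There section 13.2 adds transplanting centre where numbers allow, and the five-year Cox model adjusts for baseline imbalance, so the same criticism does not carry over unchanged.

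**Conclusion.** The point holds for DUI. The model that decides a non-randomised comparison across eras omits a baseline risk score that is already held for every offer and was designed to predict non-utilisation. A shift of 0.1 to 0.2 in mean logit-DUI would be worth an OR of about 1.08 to 1.20, or 17 to 40 livers a year against a margin of 40. This assumes slope 1 and SD 0.8 to 1.3; whether any shift occurred, and in which direction, cannot be read from the protocol.

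For NRP the conclusion is weaker. As a covariate over all offers it probably marks acceptance in part, and it can bias the OR towards no benefit if NRP uptake rose. That rests on inferred timing and assumed rates, and removing the term has its own risk of bias. It justifies showing both results, not dropping the term.

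**What to change.** 1. In section 13.2 and the SAP, add DUI to the primary model as a continuous, flexible term (for example a spline of logit-DUI) within donor type.
2. Test the 40-livers-a-year threshold on a standardised (marginal) risk difference or odds ratio from that model: 3.25 percentage points, or OR 1.20 on the marginal scale. Alternatively, re-express the conditional margin, about 1.20 to 1.26 depending on DUI spread, using control-cohort data. An adjusted OR should not be compared with an unchanged 1.20.
3. Report the primary result with and without the NRP term, and name in advance which of the two carries the decision. State in the protocol when NRP occurs relative to acceptance and how it is recorded for declined livers.

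**Cost.** No new data are needed, but both the model and the threshold are fixed in section 13.2, so this is a protocol change as well as SAP wording, and the margin must be restated before any analysis. One limitation remains: DUI was derived on offers from February 2016 to January 2020, which include the whole control period, so it is partly fitted to control outcomes. Estimating its coefficients afresh in the model does not wholly remove this, and the report should say so.

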3. SYNOPSIS

Trial Title	Utilisation of normothermi livers - a national threshold-	c machine preservation in ex-	ktended criteria	
Internal ref. no. (or short title)	Perfused Liver Utilisation Study (PLUS)			
Trial registration	ISCRTN 11552402			
Sponsor	University of Oxford			
Funder	NIHR Invention for Innovation	on Challenge Awards (NIHR20)	1003)	
Clinical Phase	Phase III			
Trial Design	Threshold-crossing design w	rith a prospectively-defined eff	ficacy threshold.	
	Control cohort (static cold storage; SCS): A priori defined real-world control cohort meeting study inclusion criteria, identified from UK Transplant Registry held by NHS Blood and Transplant (referred to as 'the registry' throughout the protocol. Study cohort (normothermic machine perfusion; NMP): Prospectively identified, consecutive liver offers with a donor utilisation index (DUI) >			
	0.27 (appendix 3), in which	NMP is made available	. ,	
Trial Participants	Extended criteria (DUI > 0.27) liver offers made to participating centres through the NHSBT offering system			
Sample Size	Control cohort: 2465 (retrospective) Study cohort: 1035 liver offers (prospectively recruited in this study)			
Planned Trial Period	Total study: 01/10/2021 – 30/09/2026 (60 months) Participant follow-up: 12 months. Long-term patient and graft survival will be assessed using registry data at 5 years post-transplant			
Planned Recruitment period	11/04/2022 – 11/10/2023 (18 months)			
·	Objectives	Outcome Measures	Timepoint(s)	
Primary	To assess whether NMP can increase the availability of livers for transplantation without compromising outcome	Functional utilisation – transplantation of the liver with 12-month patient and graft survival	12 months post- transplant	
Secondary	To assess the cost-	Intervention costs	Pre-	
	effectiveness of NMP in the context of NHS	NHS Resource Use	transplant, Day 7,	
	commissioning guidelines	Quality of Life	Months 3 and 12	
	To assess biochemical liver function in the study	Biochemical liver function (ALT, GGT, INR, Bilirubin)	Days 1-7,	
	cohort	Daily serum lactate (whilst on ITU/HDU)	Month 12	
		Model for Early Allograft Function score (MEAF)		

	To compare graft and	Primary non-function	Day 7,
	patient survival between study and control cohorts.	Graft survival (death censored)	Months 3 and 12. Long-term (5 year).
		Graft survival (non- censored)	
		Patient Survival	
	To compare the use of	Length of ITU/HDU stay	Days 1-7,

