5.5. Summary

Whilst previous studies have demonstrated efficacy and safety of NMP and suggested an increase in the proportion of livers transplanted, none have been specifically designed to quantify the impact of availability of NMP on organ utilisation. Given the additional cost and logistical burden that NMP brings over the simplicity of static cold storage, it is important to quantify the clinical and health economic impact of NMP in the NHS setting. Given the very low utilisation in extended-criteria livers with a high DUI, it would make sense to target these liver offers as the potential yield of additional transplants will be highest.

This study will achieve this by recruiting livers at the point of offering and assessing the impact of availability of NMP on the entire transplant pathway. The use of functional utilisation as a novel endpoint will assess the impact of NMP on organ utilisation and transplant rate, whilst ensuring that the additional transplants do not come at the cost of inferior clinical outcomes.

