6.2. Secondary Objectives and Outcome Measures

Objective	Outcome Measures
To assess the cost- effectiveness of NMP in the context of NHS commissioning guidelines	 NMP versus SCS intervention costs NHS resource use, measured by documentation of inpatient and outpatient episodes and treatments at study timepoints, data collected for patients on the transplant waiting list, historically published data and hospital episode statistic (HES) data; valued using standard NHS unit costs Health-related quality of life for patients on the waiting list and post-transplant, assessed by completion of the EQ-5D-5L questionnaire
To assess biochemical liver function in the study cohort	 Daily serum bilirubin, GGT, ALT and INR at days 1-7 following transplantation. Daily serum lactate at days 1-7 whilst in high level (ITU/HDU) care Serum bilirubin, ALP, ALT and AST at month 12 following transplantation. Model for Early Allograft Function (MEAF) score (9): a composite score based upon the maximum values of ALT, INR and bilirubin during the first 3 days postoperatively.
To compare graft and patient survival between study and control cohorts	 Primary non-function: graft failure during the first 10 days after liver transplantation, documented by the site team as PNF with no initial function Graft survival (death censored) at 7 days, 3 and 12 months and 5 years following transplantation (defined as a functioning transplant in the absence of death and re-transplantation). Graft survival (non-censored) at 7 days, 3 and 12 months and 5 years following transplantation (graft loss includes death or retransplantation) Patient survival at 7 days, 3 and 12 months and 5 years following transplantation.
To compare the use of postoperative hospital	 Length of stay in high level (HDU/ITU) care post-transplant Length of initial hospital stay post-transplant

resource between study and control cohorts	Need for renal replacement therapy (haemodialysis, haemofiltration, haemodiafiltration)

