8. STUDY COHORTS

8.1. Real world control (RWC) cohort

The real-world control cohort was defined in advance of recruitment of the prospective study cohort in order to minimise risk of bias in selection, and to allow the pre-defined efficacy threshold to be set.

All consecutive liver offers meeting the study inclusion and exclusion criteria defined in sections 8.3 and 8.4 between 1st January 2018 and 31st December 2019 were identified in the NHSBT transplant registry. This time period is contemporary enough to ensure stable utilisation over time, but excludes livers offered during the peaks of the coronavirus pandemic in the UK where offering and utilisation were affected by hospital capacity.

Broadly speaking, all livers with a donor utilisation index (DUI) greater than 0.27 from donors aged 16 years or over, offered to the seven participating UK liver transplant units, were eligible for inclusion. Those originating from or transplanted outside of the UK, or from Hepatitis C or HIV positive donors, were excluded. Livers that were split or reduced, that were transplanted as multi-organ transplants or where the recipient was aged <18 years were also excluded. Donor Utilisation Index was calculated using the formulae shown in Appendix 3, which differ for DBD and DCD donors. The DUI is a clinical risk score using eleven (DBD) or seventeen (DCD) donor demographic variables to predict graft utilisation. Recent analysis of UK donor data suggests that a cut-off of 0.27 represents the most poorly-utilised 60% of livers offered.

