10.2. Baseline Assessments

10.2.1. Donor and Recipient Demographics

Donor and recipient demographics will be identical to those collected for the study cohort, as described in section 9.6.1, and 9.6.2.

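### Up to 12 months, transplanted recipients in two non-concurrent cohorts are compared with no recipient covariate in the stated models, although the variables are held for both and the 5-year survival model is risk-adjusted

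*Protocol*

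**What the plan says.** - **Comparison.** Section 13.2 compares the study arm with the real-world controls "for all primary and secondary outcomes, except 5 year outcomes". One secondary objective in 6.2 is "To compare graft and patient survival between study and control cohorts", at 7 days, 3 and 12 months and 5 years. Post-operative resource use is compared as well.
- **Covariates up to 12 months.** Secondary outcomes are adjusted for donor type and NRP. Section 13.2 then adds: "when performing analyses on the subset of transplanted livers, adjustment will also be made for the transplanting centre where numbers allow". Survival is analysed by Kaplan-Meier and Cox regression, and length of stay by a competing-risks method. No recipient variable is named.
- **Covariates at 5 years.** The last paragraph of 13.2 gives the Cox model of the same survival outcomes "risk-adjustment for any imbalance in baseline characteristics that is known to affect recipient outcome". It lists no variables.
- **Data held.** Section 9.6.2 lists recipient age, sex, aetiology, indication, pre-transplant INR, creatinine, bilirubin and sodium, weight and height. For the controls, 10.2.1 says: "Donor and recipient demographics will be identical to those collected for the study cohort".
- **Periods.** In 8.1 the eligible control offers "between 1st January 2018 and 31st December 2019 were identified in the NHSBT transplant registry". The synopsis gives recruitment of the study cohort as 11 April 2022 to 11 October 2023.
- **Propensity matching.** Sections 7 and 13.4 promise a secondary propensity-matched analysis for baseline differences between the cohorts. Neither names its outcomes or its matching variables.

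**The concern.** The cohorts are neither randomised nor concurrent. The control period is centred on about the start of 2019 and the study period on about January 2023, four years later. The protocol itself gives three reasons why the recipients may differ:

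- calendar period;
- consent, which is required of study recipients (9.5, 13.4), whereas control outcomes are anonymised registry data (10.1) with no consent step described;
- which livers are transplanted, since NMP is expected to bring higher-risk livers into use (5.4).

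Donor type, NRP and centre do not capture how ill the recipient was. If recipient risk shifted between the periods, the 12-month hazard ratio and the comparisons of stay and renal replacement would carry that shift as if it were an effect of NMP. It could hide a harm or create one. Because the 5-year model adjusts for baseline imbalance and the 12-month model does not, the two hazard ratios could also differ through adjustment alone.

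**Working it through.** **1. The two survival models side by side (13.2)**

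| | Up to 12 months | 5 years |
|---|---|---|
| Outcomes | graft and patient survival | the same |
| Cohorts | study v. controls | the same |
| Named covariates | donor type, NRP, centre where numbers allow | none named; adjusted for baseline imbalance |
| Recipient risk | not included | may enter |

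The 12-month set is stated in the protocol, so this is not just detail left open.

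**2. The protocol's own figure.** It gives no sample size or power for survival. The number used below, 700 study livers, comes from 13.3 and reproduces. With margin 40/1242 = 0.0322:

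n = (1.960 + 1.282)² × [0.314 × 0.686 + (0.218 × 0.782)/3.5] / (0.314 − 0.218 − 0.0322)² ≈ 682.

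Inflation: 700/(0.75 × 0.90) = 1037, against 1035 stated.

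**3. Approximate precision of the 12-month hazard ratio**

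- Control functional utilisation is 21.8% (13.3). Utilisation for DUI > 0.27 is 26% (5.2, for 2016–2019, so a borrowed figure). Implied one-year graft survival: 0.218/0.26 = 0.838.
- Control transplants: 2465 × 0.26 = 641. Study transplants, assuming the same survival: 700 × 0.314/0.838 = 262.
- Graft losses: 641 × 0.162 ≈ 104 and 262 × 0.162 ≈ 42, total 146.
- Study share: 262/903 = 0.29. SE of the log hazard ratio ≈ 1/√(146 × 0.29 × 0.71) = 0.18.
- With survival assumed anywhere from 0.80 to 0.90, losses run from 189 to 84 and the SE from 0.16 to 0.24.

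**4. Illustrative confounding with no NMP effect.** For one binary risk factor with hazard multiplier h and prevalence p₁ (study) and p₀ (control):

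spurious HR ≈ [1 + p₁(h − 1)] / [1 + p₀(h − 1)].

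- h = 2, 30% v. 20%: 1.30/1.20 = 1.08; reversed, 0.92.
- h = 3, 35% v. 20%: 1.70/1.40 = 1.21; reversed, 0.82.

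Log shifts are 0.080 and 0.194. Against an SE of 0.16 to 0.24 these are 0.33 to 0.50 SE and 0.81 to 1.21 SE. All values of h and p are assumed, and the formula is an approximation that ignores depletion of high-risk recipients over the year.

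**5. Room for more terms.** Cohort, donor type, NRP and seven centres use 1 + 1 + 1 + 6 = 9 terms. Linear age, INR, creatinine, bilirubin and sodium add 5, and indication in four groups (assumed) adds 3, making 17. Losses per term: 146/17 = 8.6 (range 84/17 = 4.9 to 189/17 = 11.1). Stratifying by centre leaves 11 terms: 146/11 = 13.3 (range 7.6 to 17.2). This is workable for graft loss including death; patient survival and death-censored graft survival have fewer events.

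**The case against.** **Section 13 is a summary and the SAP holds the detail (13.1).** That is fair for most model detail, and I have seen only the protocol. But the protocol names a covariate set for these analyses and treats the same outcomes differently at 5 years. If the SAP already lists recipient covariates, 13.2 needs to agree with it.

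**The propensity analysis may deal with this.** One might infer that 12-month recipient outcomes get no recipient adjustment anywhere, but the text does not support that: 13.4 leaves the scope of the matching unstated and does not exclude recipient outcomes. What can be said is that a score built on all offers cannot contain recipient variables for unused livers. Even on a generous reading the matching is secondary and leaves the stated Cox model unchanged.

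**The stakes can be overstated.** A reader might infer that these comparisons carry the promise of "ensuring that the additional transplants do not come at the cost of inferior clinical outcomes". In 5.5 that phrase describes functional utilisation, and 6.1 attaches the no-compromise objective to the same endpoint. Survival is a separate secondary objective.

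**The mechanism can be overstated.** A reader might also infer that surgeons using NMP pick the recipient in the light of viability data. The protocol does not say so. Offering follows standard policy (9.1 to 9.3), an offer once made to a recipient is maintained unless the liver is unsuitable or the recipient unfit (9.5.1), and the surgeon's decision is whether to transplant (section 7).

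**Adjustment is an estimand choice.** If NMP did change recipient mix, adjusting would remove part of the strategy's effect. This stands as a reason to report both estimates. It does not justify leaving period and consent differences unadjusted.

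**Conclusion.** The point holds for the stated models. Followed as written, 13.2 gives comparisons of survival, stay and renal replacement up to 12 months that are open to confounding by recipient mix, although the variables needed to reduce it are held for both cohorts. It also handles the same survival outcomes inconsistently at 12 months and 5 years.

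The direction and size of any bias cannot be known from the protocol. The range in step 4 rests wholly on assumed prevalences and hazards. At its lower end the shift is under half a standard error; only the stronger scenario reaches about one. The precision figures also assume equal survival in both cohorts and borrow the 26% utilisation from another period. The primary analysis, its threshold and its decision rule are not affected. The change is cheap and worth making before the recipient outcomes are analysed.

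**What to change.** In 13.2, and in the SAP to match:

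1. State that the models for transplanted livers up to 12 months adjust for donor type, NRP, centre where numbers allow, and a recipient set fixed in advance: age, indication or aetiology, and pre-transplant INR, creatinine, bilirubin and sodium. Add elective or super-urgent status if the registry is confirmed to hold it for both cohorts; 8.3 mentions it, but the list in 9.6.2 does not.
2. Use the same set in the 5-year Cox model. At present no set is named there, and choice by observed imbalance should be dropped.
3. Show alongside each result the estimate adjusted only for donor type, NRP and centre.
4. Make adjustment for DUI or DLI a sensitivity analysis, because it moves the estimate from the overall effect towards a like-for-like comparison of livers.
5. Say in 13.4 which outcomes the propensity analysis covers. If it includes recipient outcomes, build that score in the transplanted subset with recipient variables.

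The cost is wording, a few more model terms and imputation of occasional missing baseline values. The named recipient variables need no new data collection; only urgency status has to be checked.
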